[Part 2 of 2 of the document. The other parts are not shown.]

Ifosfamide 3000 mg/m^2/day, IV, for 3 consecutive days (Day 1 to 3), every 21 days, for a maximum of 5 cycles.

Etoposide 100 mg/m^2/day, IV, for 3 consecutive days (Day 1 to 3), every 21 days, for a maximum of 5 cycles.

Treatment with lenvatinib will continue in 21-day cycles after chemotherapy is discontinued, until disease progression, development of unacceptable toxicity, subject request, withdrawal of consent, or discontinuation of study by the sponsor. In case the study is discontinued by the sponsor, the sponsor will continue to provide study drug (outside the study) for subjects requiring continuation of treatment.

**Control Arm (Arm B): Ifosfamide + Etoposide**

Ifosfamide 3000 mg/m^2/day, IV, daily for 3 consecutive days (Day 1 to 3), every 21 days, for a maximum of 5 cycles.

Etoposide 100 mg/m^2/day, IV, daily for 3 consecutive days (Day 1 to 3), every 21 days, for a maximum of 5 cycles.

Before dose administration on Day 1 of each cycle and prior to a change in dose due to dose reduction, the amount of lenvatinib needed for each subject must be calculated as follows:

$$\text{Scheduled dose (mg/m}^2\text{)} \times \text{body surface area (BSA) (m}^2\text{)} = \text{lenvatinib dose (mg)}$$

Body surface area (BSA) will be calculated using the method that is accepted and customarily used by the clinical site. BSA must be calculated on Day 1 of each cycle based on the subject's current height and body weight. BSA will be used to determine the amount of lenvatinib for each subject. BSA should not be corrected for amputation. The dose should be rounded to the nearest whole number. After adjustment for BSA, the daily dose of lenvatinib should not exceed 24 mg daily.

Subjects will receive study treatment as continuous 21-day cycles in both treatment arms. Treatment cycles will be counted continuously regardless of dose interruptions. If chemotherapy administration is precluded on Day 1 of a treatment cycle, the subject may resume treatment once recovered at the discretion of investigator. Subsequent chemotherapy will be administered every 21 ( $\pm 1$ ) days starting from the timepoint it was resumed.

**8.4.1.1 Lenvatinib Dose Reduction and Interruption Instructions**

Adverse events will be graded using CTCAE version 5.0.

Dose reduction and interruptions for subjects who experience lenvatinib related toxicity will be managed as described in [Table 1](#).

The starting dose of lenvatinib is 14 mg/m^2. Dose reductions occur in succession based on the previous dose level. Each dose level reduction is a 20% reduction from the previous dose.

Once the study drug dose level has been reduced, it may not be increased at a later date, unless the dose was mistakenly decreased; in this situation, the sponsor's approval is required to increase the dose.

Refer to the subsections below for management of hypertension, posterior reversible encephalopathy syndrome/reversible posterior leukoencephalopathy syndrome (PRES/RPLS), proteinuria, hepatotoxicity, thromboembolic events, hypocalcemia, gastrointestinal symptoms and acute abdominal pain, and hemorrhage, as appropriate, before consulting the dose modification table below.

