**Table 1 Criteria for Temporary Discontinuation of Study Drug, Dose Reduction, and Resumption of Treatment**

Dose Modification Guidelines for Lenvatinib Related Toxicity		
Treatment-Related Toxicitya,b	Management	Dose Adjustment
Grade 1 or Tolerable Grade 2		
	Continue treatment	No change
Intolerable Grade 2c,d or Grade 3e		
First occurrence	Interrupt lenvatinib until resolved to Grade 0-1, or tolerable Grade 2	11.2 mg/m  (or 20% reduction of the starting dose) orally QD (one-level reduction)
Second occurrence (same toxicity or new toxicity)	Interrupt lenvatinib until resolved to Grade 0-1, or tolerable Grade 2	9.0 mg/m  (or 20% reduction of the previous dose) orally QD (one-level reduction)
Third occurrence (same toxicity or new toxicity)	Interrupt lenvatinib until resolved to Grade 0-1, or tolerable Grade 2	7.2 mg/m  (or 20% reduction of the previous dose) orally QD (one-level reduction)
Fourth occurrence (same toxicity or new toxicity)	Interrupt lenvatinib	Discuss with sponsor
Grade 4f: Discontinue Study Treatment		

Note: For grading see CTCAE version 5.0. Collect all CTC grades of adverse events, decreasing and increasing grade.

BMI = body mass index, CTCAE = Common Terminology Criteria for Adverse Events

a: An interruption of study treatment for more than 28 days will require sponsor's approval before treatment can be resumed.

b: Initiate optimal medical management for nausea, vomiting, hypertension, hypothyroidism, and/or diarrhea prior to any study treatment interruption or dose reduction.

c: Applicable only to Grade 2 toxicities judged by the subject and/or physician to be intolerable.

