Lenvatinib should be withheld in any instances where a subject is at imminent risk to develop a hypertensive crisis or has significant risk factors for severe complications of uncontrolled hypertension (eg, BP  $\geq$ 99th percentile [BP  $\geq$ 160/100 mm Hg], significant risk factors for cardiac disease, intracerebral hemorrhage, or other significant comorbidities). Once the

subject has been on the same antihypertensive medications for at least 48 hours and the BP is controlled, lenvatinib should be resumed as described below.

During the Treatment Period, subjects with systolic BP  $\geq$ 99th percentile (BP  $\geq$ 160 mm Hg) or diastolic BP  $\geq$ 99th percentile (BP  $\geq$ 100 mm Hg) must have their BP monitored on Day 15 (or more frequently as clinically indicated) until systolic BP has been  $<$ 95th percentile ( $\leq$ 150 mm Hg) and diastolic BP has been  $<$ 95th percentile ( $\leq$ 95 mm Hg) for 2 consecutive treatment cycles. If a repeat event of systolic BP  $\geq$ 99th percentile (BP  $\geq$ 160 mm Hg) or diastolic BP  $\geq$ 99th percentile (BP  $\geq$ 100 mm Hg) occurs, the subject must resume the Day 15 evaluation until systolic BP has been  $<$ 95th percentile ( $\leq$ 150 mm Hg) and diastolic BP has been  $<$ 95th percentile ( $\leq$ 95 mm Hg) for 2 consecutive treatment cycles.

The following guidelines should be followed for the management of systolic BP  $\geq$ 99th percentile (BP  $\geq$ 160 mm Hg) or diastolic BP  $\geq$ 99th percentile (BP  $\geq$ 100 mm Hg) confirmed on repeat measurements after at least 30 minutes:

[figure not shown]
- Continue lenvatinib and institute antihypertensive therapy for subjects not already receiving this.
- For those subjects already on antihypertensive medication, the dose of the current agent may be increased, if appropriate, or 1 or more agents of a different class of antihypertensive should be added.
- If systolic BP  $\geq$ 99th percentile (BP  $\geq$ 160 mm Hg) or diastolic BP  $\geq$ 99th percentile (BP  $\geq$ 100 mm Hg) persists despite maximal antihypertensive therapy, then lenvatinib administration should be interrupted and restarted at a lower dose QD (one dose level reduction [20%]) only when systolic BP  $<$ 95th percentile (BP  $\leq$ 150 mm Hg) and diastolic BP  $<$ 95th percentile (BP  $\leq$ 95 mm Hg) and the subject has been on a stable dose of antihypertensive medication for at least 48 hours.

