### 6.3.1 Clinical Data on Lenvatinib in Combination with Ifosfamide and Etoposide for Treatment of Relapsed or Refractory Osteosarcoma

The safety, tolerability and activity of single-agent lenvatinib, and lenvatinib in combination with chemotherapy (ifosfamide and etoposide), have been assessed in E7080-G000-207 (Study 207), a phase 1/2, multicenter, open-label study in children, adolescents and young adults with solid tumors, including relapsed or refractory osteosarcoma, and radioiodine- refractory differentiated thyroid carcinoma. The recommended phase 2 dose (RP2D) of lenvatinib was determined in the phase 1b portion as 14 mg/m^2 orally once daily when given as single-agent as well as in combination with etoposide (100 mg/m^2 IV once daily for 3 days) + ifosfamide (3000 mg/m^2 IV once daily for 3 days), administered on days 1 to 3 of each 21-day cycle, for 5 cycles. Safety and efficacy is being assessed in the Phase 2 portion of the study.

Data from Study 207 have shown that patients with osteosarcoma may benefit from treatment with lenvatinib. In the single agent expansion cohort in relapsed/refractory osteosarcoma, (n=31; Cohort 2B), 9 of 28 evaluable patients (32.1%) achieved progression-free survival (PFS) at 4 months (PFS-4m), median PFS was 3.0 months (95% CI: 1.8, 5.5). Two out of 29 subjects (6.9%) with measurable disease had a partial response (PR) (Gaspar, et al., 2018).

Among the 31 subjects included in the safety analysis set for the single-agent lenvatinib expansion cohort, the most common adverse events were: headache (48%), vomiting (45%), decreased appetite, diarrhea, and hypothyroidism (42% each), proteinuria (39%), increased blood TSH, hypertension, nausea, pyrexia, and weight decreased (36% each). Five subjects (16.1%) discontinued treatment due to TEAEs, and 8 subjects (25.8%) reported TEAEs leading to study drug dose reduction. There were no treatment-related fatal TEAEs (Gaspar, et al., 2018).

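### For subjects at the 24 mg lenvatinib cap, the mg/m² × BSA formula and the 20% reduction rule give different reduced doses; from about 2.10 m² the formula gives no first reduction at all

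*Protocol*

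**What the plan says.** Section 8.4.1 sets the lenvatinib dose in mg as the scheduled dose in mg/m² times BSA, rounded to a whole number. The calculation is compulsory before Day 1 dosing of each cycle and also at a reduction: "prior to a change in dose due to dose reduction, the amount of lenvatinib needed for each subject must be calculated as follows". BSA is refreshed every cycle ("BSA must be calculated on Day 1 of each cycle based on the subject"), and there is a ceiling: "After adjustment for BSA, the daily dose of lenvatinib should not exceed 24 mg daily".

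Section 8.4.1.1 gives the starting dose as 14 mg/m² and defines a reduction as follows: "Each dose level reduction is a 20% reduction from the previous dose". It adds: "Once the study drug dose level has been reduced, it may not be increased at a later date", apart from a mistaken decrease corrected with sponsor approval.

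Table 1 lists the levels as 11.2, 9.0 and 7.2 mg/m². The first carries the alternative "or 20% reduction of the starting dose) orally QD (one-level reduction"; the other two carry the same alternative relative to the previous dose. Section 8.4.1.1.2 requires that, after persistent severe hypertension, lenvatinib resumes one level (20%) lower.

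Nothing in these sections says what to do when the starting dose was set by the cap.

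**The concern.** The formula and the 20% rule are two descriptions of the same step only while the dose taken equals the mg/m² level times BSA. Once the cap binds, they separate. The formula takes 20% off a notional 14 × BSA that the subject never received, so the cut from the dose actually taken is smaller than 20%. In a large enough subject it vanishes.

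Those affected are Arm A subjects at the cap with an intolerable Grade 2 or Grade 3 toxicity, or with hypertension that persists on maximal treatment. Their reduced dose depends on which sentence the site follows. In the largest subjects, the formula resumes the same 24 mg after an event for which Table 1 requires a lower one.

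**Working it through.** **Inputs.** Starting level 14 mg/m² (section 8.4.1.1); levels 11.2, 9.0 and 7.2 mg/m² (Table 1); formula, rounding and 24 mg cap (section 8.4.1); 20% rule (section 8.4.1.1); reduction frequencies (section 6.3.1); 36 subjects per arm (section 8.3).

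**1. The plan's own ladder.** 14 × 0.8 = 11.20; 14 × 0.8² = 8.96, which rounds to 9.0; 14 × 0.8³ = 7.17, which rounds to 7.2. Table 1 is a correct 20% ladder in mg/m².

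**2. Where the cap binds.** 24/14 = 1.714 m².

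**3. 20% route from 24 mg.** 24 × 0.8 = 19.2 → 19; 24 × 0.64 = 15.4 → 15; 24 × 0.512 = 12.3 → 12 mg. Multiplying each rounded dose by 0.8 gives the same (15.2 → 15; 12.0 → 12). The result does not depend on BSA.

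**4. Formula route,** min(24, rounded level × BSA):

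| BSA (m²) | Start | Level 1 | Level 2 | Level 3 | First cut |
|---|---|---|---|---|---|
| 1.8 | 24 | 20 | 16 | 13 | 16.7% |
| 1.9 | 24 | 21 | 17 | 14 | 12.5% |
| 2.0 | 24 | 22 | 18 | 14 | 8.3% |
| 2.1 | 24 | 24 | 19 | 15 | 0% |
| 2.2 | 24 | 24 | 20 | 16 | 0% |
| 20% route, any BSA at the cap | 24 | 19 | 15 | 12 | 20.8% |

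At 2.10 m², 11.2 × 2.10 = 23.52, which rounds to 24.

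**5. Thresholds.** The formula first exceeds the 20% route at 19.5/11.2 = 1.741 m² (level 1), 15.5/9.0 = 1.722 m² (level 2) and 12.5/7.2 = 1.736 m² (level 3). Between 1.714 and 1.722 m² the routes agree at every level. The first-level cut disappears from 23.5/11.2 = 2.098 m².

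**6. Next Day 1.** Suppose a site cuts a 2.0 m² subject to 19 mg. The compulsory recalculation at the same level gives 11.2 × 2.0 = 22.4 → 22 mg. The no-increase sentence protects the dose level, which has not changed, so it does not clearly forbid the rise from 19 to 22 mg.

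**7. How often reductions occur.** In Study 207 the single-agent cohort reported: "8 subjects (25.8%) reported TEAEs leading to study drug dose reduction". In the combination cohort the figure was 15 subjects (48.4%), without saying which drug was reduced. For 36 Arm A subjects this is 36 × 0.258 = 9.3 to 36 × 0.484 = 17.4, so about 9 to 17 reductions at any BSA. The number above a given BSA cannot be derived from the protocol. As an assumption only, if 3% to 10% of Arm A (about 1 to 4 subjects) had a BSA of 2.10 m² or more, then 36 × 0.03 × 0.258 = 0.3 to 36 × 0.10 × 0.484 = 1.7 subjects would meet the no-reduction case.

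**The case against.** The best counter-argument is that Table 1 already covers the cap. For an uncapped subject the bracketed 20% alternative is redundant, because 11.2 is 20% below 14. It adds something chiefly where the cap has set the mg dose. Sections 8.4.1.1 and 8.4.1.1.2 also speak of 20%, and a calculation that returns the same dose is not a reduction under either. A sensible site would give 19 mg and would not raise it later.

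That is probably what was intended, but it is not what is fixed. The alternative is joined by a bare *or* and assigned to no case, whereas the formula is compulsory. The first row refers to the starting dose, which section 8.4.1.1 defines as 14 mg/m²; 20% off that is 11.2 mg/m² again, the value that fails at the cap.

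Other points stand, and bear on size. No figure in the protocol is miscalculated; the fault lies in combining the rules. The gap is 1 mg at 1.8 m². Reaching 2.10 m² takes about 88 kg at 180 cm (2.10² × 3600/180 = 88.2, assuming the Mosteller formula; the protocol leaves the method to the site). At 2.10 m² the capped dose is already 24/2.10 = 11.4 mg/m², about 18% below 14. Treatment is interrupted until recovery, and a second event brings even the formula down to 19 mg. None of this makes an unchanged dose the reduction that Table 1 requires for toxicity at the dose actually taken.

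**Conclusion.** The concern holds. For subjects at the cap, the protocol contains two dose-reduction rules that disagree from 1.722 m² upward at one or more levels, and at the first level from 1.741 m². The first-level gap is 1 mg at 1.8 m², 3 mg at 2.0 m² and 5 mg from 2.10 m², where the formula gives 24 mg against 19 mg.

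The dose figures rest only on the protocol's levels, cap and rounding. The number of subjects affected rests on a BSA distribution that is not given. It may be small, although eligibility runs to 25 years and a Table 1 footnote provides for obese subjects. This is a patient-safety and dosing-consistency point that should be corrected; it does not alter the efficacy endpoints.

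**What to change.** Add a maximum daily dose for each level to Table 1: 24, 19, 15 and 12 mg. State in sections 8.4.1 and 8.4.1.1 that, for a subject whose dose is capped, each reduction is 20% of the mg dose actually taken, and that the Day 1 BSA recalculation may not exceed the maximum for the current level.

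Uncapped subjects are unaffected: just below 1.714 m² the formula gives at most 19.2 → 19, 15.4 → 15 and 12.3 → 12 mg, so the maxima do not bind.

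The cost is a wording amendment and lower reduced doses in large subjects than the mg/m² route gives: at the first level, 1 mg lower at 1.8 m², 3 mg at 2.0 m² and 5 mg from 2.10 m². In mg/m² terms, 19 mg at 2.10 m² is 19/2.10 = 9.0, which equals the second Table 1 level. The sponsor should confirm that this is the intended intensity.

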**Table 1 Criteria for Temporary Discontinuation of Study Drug, Dose Reduction, and Resumption of Treatment**

Dose Modification Guidelines for Lenvatinib Related Toxicity		
Treatment-Related Toxicitya,b	Management	Dose Adjustment
Grade 1 or Tolerable Grade 2		
	Continue treatment	No change
Intolerable Grade 2c,d or Grade 3e		
First occurrence	Interrupt lenvatinib until resolved to Grade 0-1, or tolerable Grade 2	11.2 mg/m  (or 20% reduction of the starting dose) orally QD (one-level reduction)
Second occurrence (same toxicity or new toxicity)	Interrupt lenvatinib until resolved to Grade 0-1, or tolerable Grade 2	9.0 mg/m  (or 20% reduction of the previous dose) orally QD (one-level reduction)
Third occurrence (same toxicity or new toxicity)	Interrupt lenvatinib until resolved to Grade 0-1, or tolerable Grade 2	7.2 mg/m  (or 20% reduction of the previous dose) orally QD (one-level reduction)
Fourth occurrence (same toxicity or new toxicity)	Interrupt lenvatinib	Discuss with sponsor
Grade 4f: Discontinue Study Treatment		

Note: For grading see CTCAE version 5.0. Collect all CTC grades of adverse events, decreasing and increasing grade.

BMI = body mass index, CTCAE = Common Terminology Criteria for Adverse Events

a: An interruption of study treatment for more than 28 days will require sponsor's approval before treatment can be resumed.

b: Initiate optimal medical management for nausea, vomiting, hypertension, hypothyroidism, and/or diarrhea prior to any study treatment interruption or dose reduction.

c: Applicable only to Grade 2 toxicities judged by the subject and/or physician to be intolerable.

d: Obese subjects with weight loss do not need to return to the baseline weight or 10% of baseline weight (ie, Grade 1 weight loss). These subjects will restart the study drug(s) at a lower dose once their weight remains stable for at least 1 week and they reached the normal BMI (if the weight loss occurred but it is still above normal BMI, they can restart the study treatment at a lower dose once the weight has been stable for at least 1 week). Normal BMI should be used as the new baseline for further dose reductions. Obesity is defined as body mass index (BMI) percentiles corresponding to 30 kg/m^2, related to the age of the children (Cole, et al., 2000) or BMI  $\geq$  the 95th percentile for children and teens of the same age and sex (Ogden, et al., 2002) (Appendix 8 and Appendix 9).

e: For asymptomatic laboratory abnormalities, such as Grade  $\geq 3$  elevations of amylase and lipase that are not considered clinically relevant by the investigator, continuation of treatment should be discussed with the Sponsor.

f: Excluding laboratory abnormalities judged to be non-life-threatening, in which case manage as Grade 3.

#### 8.4.1.1.1 BLOOD PRESSURE

For children, blood pressure varies by the sex and age of the child and it is closely related to height and weight. Blood pressure will be assessed in terms of percentile for sex, age and height/length. Guidelines to sex, age, and height-specific percentiles of blood pressure are provided in Appendix 6 and Appendix 7. Blood pressure that is consistently above the 95th percentile [for subjects age 18 to 25 years BP  $\leq$  140/90 mm Hg] for age and height/length

requires further evaluation. A referral to a cardiologist is recommended for patients who develop hypertension during the study. Ideally, cardiovascular assessments and the management of hypertension should be supervised by a cardiologist. Exercise, excitement, coughing, crying, and struggling may raise the systolic pressure of children as much as 40 to 50 mmHg greater than their usual level. Variability in blood pressure in children of approximately the same age and body build should be expected and serial measurements should always be obtained when evaluating a patient with hypertension.

#### 8.4.1.1.2 MANAGEMENT OF HYPERTENSION

Hypertension is a recognized side-effect of treatment with drugs inhibiting VEGF signaling. Investigators should therefore ensure that subjects enrolled to receive treatment with lenvatinib have BP <95th percentile [BP  $\leq$ 150/90 mm Hg] for sex, age, and height/length at the time of study entry and, if known to be hypertensive, have been on a stable dose of antihypertensive therapy for at least 1 week before Cycle 1 Day 1. Early detection and effective management of hypertension are important to minimize the need for lenvatinib dose interruptions and reductions.

Regular assessment of BP should be conducted as detailed in the Schedule of Procedures/Assessments ([Table 5](#) and [Table 6](#)). Hypertension will be graded using CTCAE v5.0, based on BP measurements only (and not on the number of antihypertensive medications).

If the subject's initial BP measurement is elevated (systolic BP  $\geq$ 95th percentile [BP  $\geq$ 140 mm Hg] or diastolic BP  $\geq$ 95th percentile [BP  $\geq$ 90 mm Hg]), the BP measurement should be repeated at least 5 minutes later. The mean value of 2 measurements at least 5 minutes apart is defined as 1 BP assessment. If the BP assessment (ie, the mean of the 2 BP measurements obtained at least 5 minutes apart) is elevated (systolic BP  $\geq$ 140 mm Hg or diastolic BP  $\geq$ 90 mm Hg), a confirmatory assessment should be obtained at least 30 minutes later by performing 2 measurements (at least 5 minutes apart) to yield a mean value.

Antihypertensive agents should be started as soon as elevated BP (systolic BP  $\geq$ 95th percentile [BP  $\geq$ 140 mm Hg] or diastolic BP  $\geq$ 95th percentile [BP  $\geq$ 90 mm Hg]) is confirmed on 2 assessments obtained 30 minutes apart. The choice of antihypertensive treatment should be individualized to the subject's clinical circumstances and follow standard medical practice. For previously normotensive subjects, monotherapy with one of the classes of antihypertensives should be started when systolic BP  $\geq$ 95th percentile [BP  $\geq$ 140 mm Hg] or diastolic BP  $\geq$ 95th percentile [BP  $\geq$ 90 mm Hg] is first observed on 2 assessments obtained 30 minutes apart. For those subjects already on antihypertensive medication, treatment modification may be necessary if hypertension persists.

Lenvatinib should be withheld in any instances where a subject is at imminent risk to develop a hypertensive crisis or has significant risk factors for severe complications of uncontrolled hypertension (eg, BP  $\geq$ 99th percentile [BP  $\geq$ 160/100 mm Hg], significant risk factors for cardiac disease, intracerebral hemorrhage, or other significant comorbidities). Once the

subject has been on the same antihypertensive medications for at least 48 hours and the BP is controlled, lenvatinib should be resumed as described below.

During the Treatment Period, subjects with systolic BP  $\geq$ 99th percentile (BP  $\geq$ 160 mm Hg) or diastolic BP  $\geq$ 99th percentile (BP  $\geq$ 100 mm Hg) must have their BP monitored on Day 15 (or more frequently as clinically indicated) until systolic BP has been  $<$ 95th percentile ( $\leq$ 150 mm Hg) and diastolic BP has been  $<$ 95th percentile ( $\leq$ 95 mm Hg) for 2 consecutive treatment cycles. If a repeat event of systolic BP  $\geq$ 99th percentile (BP  $\geq$ 160 mm Hg) or diastolic BP  $\geq$ 99th percentile (BP  $\geq$ 100 mm Hg) occurs, the subject must resume the Day 15 evaluation until systolic BP has been  $<$ 95th percentile ( $\leq$ 150 mm Hg) and diastolic BP has been  $<$ 95th percentile ( $\leq$ 95 mm Hg) for 2 consecutive treatment cycles.

The following guidelines should be followed for the management of systolic BP  $\geq$ 99th percentile (BP  $\geq$ 160 mm Hg) or diastolic BP  $\geq$ 99th percentile (BP  $\geq$ 100 mm Hg) confirmed on repeat measurements after at least 30 minutes:

[figure not shown]
- Continue lenvatinib and institute antihypertensive therapy for subjects not already receiving this.
- For those subjects already on antihypertensive medication, the dose of the current agent may be increased, if appropriate, or 1 or more agents of a different class of antihypertensive should be added.
- If systolic BP  $\geq$ 99th percentile (BP  $\geq$ 160 mm Hg) or diastolic BP  $\geq$ 99th percentile (BP  $\geq$ 100 mm Hg) persists despite maximal antihypertensive therapy, then lenvatinib administration should be interrupted and restarted at a lower dose QD (one dose level reduction [20%]) only when systolic BP  $<$ 95th percentile (BP  $\leq$ 150 mm Hg) and diastolic BP  $<$ 95th percentile (BP  $\leq$ 95 mm Hg) and the subject has been on a stable dose of antihypertensive medication for at least 48 hours.
  - If systolic BP  $\geq$ 99th percentile (BP  $\geq$ 160 mm Hg) or diastolic BP  $\geq$ 99th percentile (BP  $\geq$ 100 mm Hg) recurs on the first dose reduction despite optimal management of hypertension with antihypertensive medications (either by dose increase or the addition of a different class of antihypertensive), then lenvatinib administration should be interrupted and restarted at an additional dose reduction only when systolic BP  $<$ 95th percentile (BP  $\leq$ 150 mm Hg) and diastolic BP  $<$ 95th percentile (BP  $\leq$ 95 mm Hg) and the subject has been on a stable dose of antihypertensive medication for at least 48 hours.
  - If systolic BP  $\geq$ 99th percentile (BP  $\geq$ 160 mm Hg) or diastolic BP  $\geq$ 99th percentile (BP  $\geq$ 100 mm Hg) recurs on the second dose reduction despite optimal management of hypertension with antihypertensive medications (either by dose increase or the addition of a different class of antihypertensive), then lenvatinib administration should be interrupted and restarted at a third dose reduction only when systolic BP  $<$ 95th percentile (BP  $\leq$ 150 mm Hg and diastolic BP  $<$ 95th percentile (BP  $\leq$ 95 mm Hg) and the participant has been on a stable dose of antihypertensive medication for at least 48 hours.

- Additional dose reduction should be discussed with the Sponsor.

The following guidelines should be followed for the management of Grade 4 hypertension (life-threatening consequences):

- Institute appropriate medical management
- Discontinue lenvatinib

Figure 2 shows the procedures associated with the management of hypertension.

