#### 8.5.1.4.4 VITAL SIGNS AND WEIGHT MEASUREMENTS

Vital sign measurements (ie, systolic and diastolic blood pressure [BP] [mmHg], pulse [beats per minute], respiratory rate [per minute]), body temperature (in centigrade), weight (kg), and height (cm) will be obtained at the visits designated in the Schedule of Assessments ([Table 5](#) and [Table 6](#)) by a validated method. Blood pressure and pulse will be measured after the subject has been resting for 5 minutes. All BP measurements should be performed on the same arm, preferably by the same person. On Cycle 1 Day 8, subjects will be contacted by telephone to assess for the development of early toxicity. Subjects will be provided with a BP cuff to monitor BP at home or can have the measurement done by a local healthcare provider, and will report the C1D8 measurement at telephone contact. An unscheduled visit can occur prior to C1D15 if deemed necessary by the investigator.

Only 1 BP measurement is needed for subjects with systolic BP <95th percentile (BP <140 mm Hg) and diastolic BP <95th percentile (BP <90 mmHg). If the subject's initial BP measurement is elevated (systolic BP  $\geq$ 95th percentile [ $\geq$ 140 mmHg] or diastolic BP  $\geq$ 95th percentile [ $\geq$ 90 mmHg]), the BP measurement should be repeated at least 5 minutes later. The mean value of 2 measurements at least 5 minutes apart is defined as 1 BP assessment. If the BP assessment (ie, the mean of the 2 BP measurements obtained at least 5 minutes apart) is elevated (systolic BP  $\geq$ 95th percentile [ $\geq$ 140 mm Hg] or diastolic BP  $\geq$ 95th percentile [ $\geq$ 90 mm Hg]), a confirmatory assessment should be obtained at least 30 minutes later by performing 2 measurements (at least 5 minutes apart) to yield a mean value.

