- h. A comprehensive physical examination (including a neurological examination) will be performed at the Screening and Baseline Visits (only if screening physical examination was performed  $>7$  days prior to C1D1), C1D15, C2D1, C2D15, and Day 1 visit of each subsequent cycle, and at the Off-treatment Visit. A symptom-directed physical examination will be performed on C1D1 and at any time during the study, as clinically indicated.
- i. Assessments will include vital signs (resting BP, HR, RR, and body temperature) and weight. Blood pressure that is consistently above the 95th percentile for sex, age, and height/length requires further evaluation. Refer to hypertension management guidelines in [Section 8.4.1.1.2](#).
- j. On Cycle 1 Day 8, subjects will be contacted by telephone to assess for the development of early toxicity. Subjects will be provided with a BP cuff to monitor BP at home or can have the measurement done by a local healthcare provider, and will report the C1D8 measurement at telephone contact. An unscheduled visit can occur prior to C1D15 if deemed necessary by the investigator.
- k. Single 12-lead ECG. If possible, subjects must be in the recumbent position for a period of 5 minutes prior to the ECG. ECG should be conducted at

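### Section 8.4.1.1.2 decides on confirmatory blood pressure by the adult 140/90 mm Hg cut-off alone, where Section 8.5.1.4.4 uses the 95th percentile for the same step in children

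*Protocol*

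**What the plan says.** Section 8.4.1.1.2 sets out a chain of three steps.

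1. **Initial reading.** If it is at or above the 95th percentile [140 systolic or 90 diastolic], "the BP measurement should be repeated at least 5 minutes later". The mean of the two readings counts as one assessment.
2. **Averaged assessment.** The condition is a mean systolic of at least 140 or a mean diastolic of at least "90 mm Hg), a confirmatory assessment should be obtained at least 30 minutes later by performing 2 measurements (at least 5 minutes apart"). No percentile appears here.
3. **Treatment start.** Antihypertensives begin once blood pressure at or above the 95th percentile [140 or 90] "is confirmed on 2 assessments obtained 30 minutes apart".

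Section 8.5.1.4.4 describes step 2 in almost the same terms, but its condition is the 95th percentile with the adult value in brackets: "90 mm Hg]), a confirmatory assessment should be obtained at least 30 minutes later by performing 2 measurements (at least 5 minutes apart"). Section 8.4.1.1.1 states the general rule for children: "Blood pressure will be assessed in terms of percentile for sex, age and height/length".

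Footnote i to Table 5 directs sites to the section with the bare cut-off: "Refer to hypertension management guidelines in" Section 8.4.1.1.2. The protocol file contains the body text twice, and the mismatch is the same in both copies.

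**The concern.** Two sections give different thresholds for the same act at the bedside. Under the literal text of Section 8.4.1.1.2, a child whose mean is at or above the 95th percentile but below 140/90 does not reach the confirmatory assessment. Treatment for that child nevertheless depends on a second assessment having been done. A site that works from the hypertension section alone could stop after step 2 and never reach the treatment decision.

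This matters because hypertension is a recognised effect of VEGF inhibition. Section 6.3.1 reports it in 36% of the 31 subjects in the single-agent lenvatinib cohort. At least 32 of about 72 subjects must be under 18. Section 8.4.1.1.2 itself says that early detection and good control help to limit lenvatinib interruptions and reductions.

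**Working it through.** No sample-size or error-rate figure bears on this. The check compares the texts and then looks up the protocol's own percentile tables.

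**Thresholds side by side**

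| Step | Section 8.4.1.1.2 | Section 8.5.1.4.4 |
|---|---|---|
| Initial reading, repeat after 5 minutes | ≥95th percentile [≥140 / ≥90] | ≥95th percentile [≥140 / ≥90] |
| Mean of two readings, confirm after 30 minutes | ≥140 / ≥90 only | ≥95th percentile [≥140 / ≥90] |
| Start antihypertensives | ≥95th percentile [≥140 / ≥90], two assessments | not covered |

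Only the middle step of Section 8.4.1.1.2 lacks the percentile. The steps before and after it both have it, which suggests an omission and not a deliberately different rule.

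**Two examples from Appendix 6**

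- Boy aged 15, median height: 95th percentile 131/83, 99th percentile 138/91. Take a mean of 135/85. It is above the 95th percentile (135 > 131, 85 > 83), below 140/90, and below the 99th percentile (135 < 138, 85 < 91). Section 8.5.1.4.4 requires confirmation; step 2 of Section 8.4.1.1.2 does not.
- Boy aged 10, median height: 95th percentile 119/80, 99th percentile 127/88. A mean of 125/84 falls in the same gap.

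**How wide the gap is in the tables**

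Inputs: the 95th- and 99th-percentile rows of Appendices 6 and 7, ages 2 to 17. That is 16 ages × 7 height columns × 2 sexes = 224 cells, unweighted. A cell counts if systolic is below 140 and diastolic below 90. The distance is 140 minus the 95th-percentile systolic and 90 minus the 95th-percentile diastolic, with medians taken separately.

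| Ages | Cells | 95th percentile below both | 99th percentile below both | Median distance, 95th percentile to 140/90 (mm Hg) |
|---|---|---|---|---|
| 2–9 | 112 | 112 | 112 | 28 / 17 |
| 10–13 | 56 | 56 | 44 | 18 / 10 |
| 14–17 | 56 | 55 | 10 | 10.5 / 6 |
| All | 224 | 223 | 166 | – |

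The single 95th-percentile exception is boys aged 17 in the tallest height column, where the systolic value is 140. At ages 14 to 17 the 99th-percentile systolic is still below 140 in 42 of 56 cells (girls 28 of 28, boys 14 of 28), so at those ages the gap at the 99th percentile is mainly isolated systolic elevation.

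**Does the gap extend to the 99th percentile and above in practice?** Mainly not. Section 8.4.1.1.2 has separate rules there that do not run through step 2. Withholding and Day 15 monitoring state no confirmation requirement, and the management list has its own: "confirmed on repeat measurements after at least 30 minutes". The exposed range is therefore mainly the 95th to below the 99th percentile.

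**The case against.** The best reply is that this is an omission and not a pair of opposing orders. Section 8.4.1.1.2 does not forbid confirmation below 140/90, so a site can satisfy both sections by following Section 8.5.1.4.4. The hypertension section also points the right way: it uses the 95th percentile for an elevated initial reading just before the faulty step, and its treatment rule just after cannot be applied to a child without the second assessment. Footnote i itself says that pressure consistently above the 95th percentile needs further evaluation, and Section 8.4.1.1.1 asks for serial measurements when hypertension is being evaluated. Many sites will infer what was meant.

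The table count can also be criticised. It is unweighted and half the cells are ages 2 to 9, whereas Section 6.1 places the incidence peak at 15 to 19 years. Subjects aged 18 to 25 are not affected. The 99th-percentile counts describe children whom other rules already protect. Figure 2 may carry the correct threshold.

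Much of this stands as a limit on the consequence. Inference by sites makes harm less likely, the 14–17 row is the more relevant one, and the 99th-percentile counts do not enlarge the exposed range. It does not remove the defect: the section that sites are sent to for hypertension management gives a higher threshold than the measurement section for children at this step, and a safety trigger should not rest on inference. A correct Figure 2 would still leave the text contradicting it.

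**Conclusion.** The concern holds. The averaged-assessment step in Section 8.4.1.1.2 conflicts with Section 8.5.1.4.4 and does not deliver the second assessment that its own treatment rule needs in children below 140/90. In the protocol's tables the conflict covers nearly the whole paediatric range (223 of 224 cells at the 95th percentile), with a typical distance of 10.5/6 mm Hg at ages 14 to 17 and more at younger ages.

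The conclusion rests on the literal text. Figure 2 was not available, so its threshold is unchecked. The protocol does not give the trial's age mix, so no share of subjects can be stated. Randomisation, the primary endpoint, error rates and power are unaffected. It should be corrected.

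**What to change.** In Section 8.4.1.1.2, change the condition on the averaged assessment to systolic BP ≥95th percentile [≥140 mm Hg] or diastolic BP ≥95th percentile [≥90 mm Hg], as Section 8.5.1.4.4 already has it. Check that Figure 2 shows the same threshold.

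The cost is a one-line correction in the next amendment and some additional repeat readings at site visits.
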